4.1 OVERVIEW OF STUDY DESIGN/INTERVENTION

4.2 Design

The proposed study is a randomized controlled trial study. The primary aim of this study is to assess the feasibility of an automated geriatric co-management program for perioperative management of patients with solid mass or nodule who present to MSKCC Surgery Service clinics, and being considered for surgery.

Secondary aims are to collect preliminary data on its impact on postoperative adverse surgical outcomes, and functional recovery compared to in-person geriatric co-management.

The first visit (surgery clinics when patients are being considered for surgical resection of their solid mass or nodule suspicious for cancer): In surgery clinics, all patients complete the eRFA as a routine care.

Inclusion criteria are: 1) solid mass or nodule suspicious for cancer, 2) aged 65 or older, 3) being considered for surgical resection of the solid mass or nodule with anticipated hospital length of stay of at least two days, 4) completed eRFA.

Exclusion criteria: 1) unable to read or comprehend English, 2) not having a completed eRFA within the two months of undergoing surgery, 3) being discharged in one day or earlier from the hospital.

Note) To avoid excluding patients based on item 2, patients have to complete another eRFA within two months of surgery.

Following patients' consent to participate in the study, patients will also complete a 4-Meter walk test (4MVMT)[31]. Their sociodemographic characteristics will also be recorded.

Subsequently, they will be randomized either to in-person geriatric co-management or the automated geriatric co-management program, using MSKCC's Clinical Research Database, a secure randomization system ensuring full allocation concealment.

The automated geriatric co-management program group: Through literature review, consideration of American College of Surgeons and American Geriatrics Society recommendation[32], and our years of collective experience for postoperative care for older adults with cancer, we have developed perioperative geriatric recommendations for each of the 12 eRFA impairments and comorbid conditions (appendix 1).

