intervention will be deemed feasible if recommendations are followed for 50 patients. Finally, we will present the distribution of number of recommendations made and followed in the automated geriatric comanagement arm.

Secondary Aims

Effect of the automated geriatric co-management program compared to the in-person geriatric co-management on adverse surgical events.

All between-group comparisons will be by modified intent-to-treat (complete case analysis), with patients analyzed according to randomization, irrespective of whether they were proceeded to automated geriatric co-management or in-person geriatric co-management. To compare, by intervention arm, the proportion of patients with a composite outcome ("adverse surgical event") of either surgical complications grade 2 or higher, or prolonged hospital length of stay, or discharge to another care facility rather than home, or 30-day readmission to the hospital. Prolonged hospital length of stay will be defined as hospital length of stay greater than 75% of the cohort who underwent the similar procedure. We will test the association between intervention arm and adverse surgical event using logistic regression with the randomization stratum as the covariate.

It is plausible that the relative value of in-person vs. automated geriatric *co-management* depends on baseline risk, for instance, it could be that average risk patients are adequately managed by the automated approach, but those at high risk require individualized care. To this end, we will use a logistic regression with adverse surgical event as the outcome, study arm as the predictor, randomization strata as the covariate, and adjust for continuous baseline risk using the MSK-FI, with restricted cubic splines with knots at the tertiles to allow for non-linearity. We will then visualize the risk in both intervention arms across baseline risk to provide an individualized estimate of benefit for a given level of baseline deficit. The MSK-FI is a frailty index defined by ten sets of comorbidities, and one component related to dependency on five activities of daily living. The former will be queried from the institutional database, and the latter is assessed using the bADL and iADL measures on the eRFA.[35]

Effect of the automated geriatric co-management program with in-person geriatric co-management on postoperative functional recovery.

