We are additionally interested in using the three components, of the patient-reported functional recovery in three categories: complete recovery (defined as all three post-operative measurement score being greater than or equal to the pre-operative measurement score), partial recovery (defined as at least one, but not all three, post-operative measurement scores being greater than or equal to the pre-operative measurement score), or no recovery (defined as none of the post-operative measurement scores being greater than or equal to the pre-operative measurement score). Similarly we will use two components of the clinician-evaluate functional recovery to define three categories: complete recovery (defined as all both post-operative measurement score being greater than or equal to within 10% of the pre-operative measurement score), partial recovery (defined as at least one, but not both, post-operative measurement scores being greater than or equal to within 10% of the pre-operative measurement score), or no recovery (defined as neither of the post-operative measurement scores being greater than or equal to within 10% of the pre-operative measurement score). We will test the association between intervention arm and degree of recovery by using ordinal regression with randomization strata as covariates.

As it is likewise plausible that the relative value of in-person vs. automated geriatric co-management depends on baseline risk, we will repeat the analysis described above, related to baseline risk, for the outcomes of patient-reported functional recovery and clinician-assessed functional recovery.

Sample size

With a null hypothesis of 55% and the alternative hypothesis of 70% of patients with recommendations followed, and a one-sided α of 5% and a power of 85%, we require 77 eligible patients to be accrued in the automated geriatric co-management arm for a two-stage Simon minimax design. We expect about 25% of patients to be excluded for the primary aim due to no impairment (5%) or crossover to the in-person

geriatric comanagement arm (20%) suggesting a total accrual close to 100 per group.

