Assuming a correlation of 0.5 between baseline and follow-up, and a standard deviation of 1.8 (as seen in our preliminary dataset for the basic activities of daily living, the score of which ranges from 0 to 14), with ~95 patients per arm (after an estimated 5% loss of patients due to drop out), the power for various effect sizes for our continuous secondary endpoints when analyzed using ANCOVA are shown in the table, where it can be seen that we have high power to detect small differences between groups. Sensitivity analyses will be conducted where missing outcome data will be imputed by Multiple Imputation using Chained Equations.

Difference between groups	Power
0.5	60%
0.67	84%
0.8	94%

In 2017, the surgical services had completed surgical procedures on more than 5000 patients aged 65 or older with a hospital length of stay of 2 days or longer. Therefore, we expect to enroll the 200 patients for our study in less than two-years. We expect most patients to be older (75+) but to ensure that younger patients are not overly represented, we will cease accrual of patients 65 – 74 after 60 are accrued (i.e. 30%).

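### The baseline-risk analysis asks whether the arm effect changes with MSK-FI, but its model only adjusts for MSK-FI and so fixes one arm odds ratio at every risk level

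*Combined protocol and SAP*

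**What the plan says.** Section 11.0, under the adverse-surgical-event aim, raises the possibility that the better approach differs by patient risk. Its example is that "average risk patients are adequately managed by the automated approach, but those at high risk require individualized care". To examine this it specifies a logistic regression for the composite event with "study arm as the predictor, randomization strata as the covariate, and adjust for continuous baseline risk using the MSK-FI". MSK-FI enters through "restricted cubic splines with knots at the tertiles to allow for non-linearity". Risk is then to be plotted for both arms across baseline risk "to provide an individualized estimate of benefit for a given level of baseline deficit".

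For functional recovery, the same section gives the same motivation and says "we will repeat the analysis described above, related to baseline risk", for both the patient-reported and the clinician-assessed outcomes.

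Neither document section names a product term, a separate spline or model for each arm, or a test of effect modification. The randomization strata also enter only as covariates, so they do not let the arm effect vary either.

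**The concern.** Whether the relative value of two treatments depends on baseline risk is a question of effect modification. A model with arm and MSK-FI as separate terms assumes the answer is no on the odds-ratio scale. The spline bends the risk curve but bends it identically in both arms on the logit scale.

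The resulting figure would still look individualized. The vertical distance between the two curves changes somewhat with MSK-FI because of the logit transformation, and a reader could take that as evidence that benefit varies with risk. If the plan's own example were true, the figure would tend to show a gap for lower-risk patients where there is none and understate the gap for high-risk patients.

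**Working it through.** The plan attaches no figure to this analysis, so there is none to reproduce. The check is first algebraic, then an illustration on assumed inputs.

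**1. Structure.** Write A = 1 for automated, 0 for in-person, and M for MSK-FI.

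- As written: logit P = a + b·A + strata + s(M). At fixed M and stratum, the arm log odds ratio is b, so the odds ratio is exp(b) for every M. If b = 0 there is no gap anywhere; if b ≠ 0 there is a gap of the same sign everywhere.
- With a product term: logit P = a + b·A + strata + s(M) + g·A·M. The arm log odds ratio is b + g·M, which can be near zero at one risk level and large at another.

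**2. Illustration.** Inputs:

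- 190 patients, from 2 × 95 (Sample size: "with ~95 patients per arm (after an estimated 5% loss of patients due to drop out").
- Assumed, because the documents do not give them: M Poisson with mean 3; in-person risk 40% at M = 3; log-odds slope 0.25 per MSK-FI point; true log odds ratio ln(3) × (M − 1)/5, so OR 1 at M = 1 and OR 3 at M = 6. Strata are omitted and M is linear.

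Truth:

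- M = 1: logit(0.40) − 2 × 0.25 = −0.905, risk 28.8% in both arms, gap 0.
- M = 6: −0.405 + 3 × 0.25 = 0.345, in-person risk 58.5%. Automated odds are 1.411 × 3 = 4.23, risk 80.9%, gap 22.4 points.

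Large-sample fit of the written model: a single odds ratio of 1.55.

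| MSK-FI | True gap | Fitted in-person risk | Fitted automated risk | Plotted gap |
|---|---|---|---|---|
| 1 | 0 | 24.6% | 33.6% | 9.0 points |
| 6 | 22.4 points | 65.5% | 74.6% | 9.2 points (before rounding) |

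**3. Range.** Varying mean MSK-FI (2, 3), risk at the mean (30, 40, 50%) and slope (0.1, 0.25, 0.4), with the true odds ratio still 1 to 3:

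- single odds ratio 1.21–1.63;
- plotted gap at MSK-FI 1 of 4.6–10.3 points (truth 0);
- plotted gap at MSK-FI 6 of about 1.9–11.7 points (truth 10.5–26.8).

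With weaker modification (OR 1 to 2, other base inputs unchanged), the same calculation gives a single odds ratio of 1.33, a gap of 5.8 points at MSK-FI 1 (truth 0) and 6.3 at MSK-FI 6 (truth 15.3, from odds 1.411 × 2 = 2.82, risk 73.8%, minus 58.5%).

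**4. What the product term would deliver.** Base case, 2,000 simulated trials of 190 patients:

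- mean odds ratios 1.00 at MSK-FI 1 and 3.09 at MSK-FI 6;
- typical 95% intervals 0.38–2.69 and 0.82–11.69;
- interaction power 19–21%, and 13–23% over the grid in step 3;
- power by total sample size: 53% at 600, 64% at 800, 75% at 1,000, 81% at 1,200;
- with a constant true odds ratio of 1.5, the interaction is rejected in 4.1–4.8% of trials, as it should be at a 5% level.

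**5. Knots.** A restricted cubic spline with k knots uses k − 1 columns. Tertiles give two cut-points. If those are the only knots, there is one column, a straight line, and no non-linearity is allowed. With boundary knots added there are four knots and three columns. The plan does not say which is meant.

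**The case against.** The strongest case has four parts.

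- **Reading.** Adequate management at average risk need not mean exactly zero difference, and the planned display is of absolute risk. A constant odds ratio applied over a risk score is a recognised way to produce individual absolute estimates. An interaction may also have been intended and simply left out.
- **Hypothetical size.** The range in step 3 mostly holds the true odds ratio at 1 to 3, which is strong modification. Weaker modification gives smaller distortion.
- **Noise at this sample size.** In the base case with 190 patients, the written model's arm odds ratio has a 95% interval that includes 1 in 69% of trials. A figure with bands would often not support any gap.
- **The remedy costs precision.** Root-mean-square error of the plotted gap, in points, written model against product-term model:

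| True OR, MSK-FI 1 to 6 | At MSK-FI 1 | At MSK-FI 6 |
|---|---|---|
| 1 to 3 | 11.1 v 10.2 | 14.6 v 13.1 |
| 1 to 2 | 8.4 v 10.1 | 11.4 v 13.6 |
| 1 to 1.5 | 7.2 v 9.8 | 8.9 v 14.0 |
| constant 1.5 | 6.7 v 10.5 | 6.9 v 14.4 |

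The precision points stand. Unless modification is large, the product term's extra variance outweighs the bias it removes, and the trial will seldom settle the question. They do not rescue the written model, whose better precision comes from assuming away the effect under study. The absolute-risk reading serves the stated question poorly: in the base case the additive gap moves only from 9.0 to 9.2 points. If an interaction was intended, an analyst following the text would still not fit it, and adding it after seeing the data would be an unplanned choice.

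**Conclusion.** The concern holds. Followed as written, the analysis estimates one arm odds ratio and cannot answer whether that ratio depends on baseline risk. That conclusion is algebraic and needs no assumption. The same constraint carries over to the repeated recovery analyses if no product term is added there.

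The size of the distortion does rest on assumptions, above all on how strongly the effect varies: about 9 points too high at MSK-FI 1 and 13 points too low at MSK-FI 6 (22.4 − 9.2 = 13.2) in the base case, and less with weaker modification.

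The matter is moderate and should be fixed. The primary feasibility aim and the main between-arm test do not depend on it, no decision rule uses it, and section 4.2 frames the purpose modestly: "Secondary aims are to collect preliminary data on its impact on postoperative adverse surgical outcomes". The knot question is a minor clarification.

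**What to change.** In section 11.0:

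- Add an arm-by-MSK-FI term to the baseline-risk model and to its repeats for both recovery outcomes. A linear product term is preferable with about 190 patients; arm-by-spline terms would cost more precision.
- Report the interaction estimate with its 95% confidence interval. Plot arm-specific risk and the arm difference, both with confidence bands.
- Label the analysis exploratory and state that power is low, so a non-significant interaction must not be read as a uniform effect.
- If an additive-model plot is also shown for its better precision, say that it assumes a constant odds ratio.
- State the knots: at least three, or the tertiles as interior knots with boundary knots added.

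The cost is one model term per analysis and a few sentences, with no new data. The bands will be wide. A linear term also only approximates a threshold: if the true odds ratio were 1.0 below MSK-FI 4 and 2.46 from 4 upwards, it would return about 0.87 at MSK-FI 1 and 2.7 at MSK-FI 6.

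### The MSK-FI spline is a straight line if its only knots are the tertiles, and with no arm-by-MSK-FI term the model cannot show whether the arms' relative value depends on baseline risk

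*Combined protocol and SAP*

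**What the plan says.** Section 11.0 (Secondary Aims) raises the possibility that the relative merit of automated and in-person co-management varies with the patient's baseline risk. To examine this, the plan states: "we will use a logistic regression with adverse surgical event as the outcome, study arm as the predictor, randomization strata as the covariate". It then says it will "adjust for continuous baseline risk using the MSK-FI", "with restricted cubic splines with knots at the tertiles to allow for non-linearity". The output is a plot: "We will then visualize the risk in both intervention arms across baseline risk", intended to give an estimate of benefit specific to a patient's level of deficit.

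The index is described as follows: "The MSK-FI is a frailty index defined by ten sets of comorbidities, and one component related to dependency on five activities of daily living". No score range is given for it.

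Later in the same section the approach is carried over to recovery: "we will repeat the analysis described above, related to baseline risk, for the outcomes of patient-reported functional recovery and clinician-assessed functional recovery".

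The plan gives no number of knots, no degrees of freedom, no mention of boundary knots and no term combining arm with MSK-FI.

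**The concern.** Two parts of the specification do not fit their purpose.

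- **Knots.** A restricted cubic spline is forced to be linear beyond its outermost knots. Two knots leave no room for curvature, so the literal wording asks for non-linearity and describes a line.
- **Interaction.** Whether relative value depends on baseline risk is a question of effect modification. A model that adjusts for MSK-FI without letting the arm effect vary with it assumes the answer.

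The deliverable is a pair of plotted risk curves meant to inform individual patients, so their form is the substance of the analysis. If that form is left to a software convention, an analyst could fit a 1-df line or a 3-df curve, even after seeing the data, and still be within the plan. The specification is reused, so three outcomes are affected: adverse surgical events, patient-reported recovery and clinician-assessed recovery.

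**Working it through.** The plan states no figure for this spline, so there is nothing to reproduce. The check is on the algebra and on the rank of the spline basis.

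**Inputs.** From section 11.0: restricted cubic spline, knots at the tertiles (two points, a < b), logistic model, arm as predictor, randomization strata as covariate. Assumed for illustration only: an MSK-FI range of 0 to 11 with tertiles at 2 and 4. The algebra in step 1 does not depend on these values.

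**Step 1: two knots.** Below a the curve is linear, so it can be written

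f(x) = b0 + b1·x + c1·(x − a)³₊ + c2·(x − b)³₊.

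Above b, the coefficient of x³ is c1 + c2 and that of x² is −3(a·c1 + b·c2). Linearity in the upper tail needs both to be zero:

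- c1 + c2 = 0
- a·c1 + b·c2 = 0

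The determinant of this system is b − a (here 4 − 2 = 2), which is not zero, so c1 = c2 = 0. What remains is b0 + b1·x: 1 df and no non-linear terms.

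**Step 2: degrees of freedom by reading.** With K knots the spline uses K − 1 df, of which K − 2 are non-linear. As a numerical check, each basis was fitted to the test curve y = 0.05(x − 3)² at 200 points on 0 to 11. A straight line leaves a residual sum of squares of 41.49.

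| Knot set | Knots | df | Non-linear terms | Residual sum of squares |
|---|---|---|---|---|
| Tertiles only (2, 4) | 2 | 1 | 0 | 41.49 |
| Three knots (1, 3, 5) | 3 | 2 | 1 | 8.30 |
| Tertiles plus boundary knots (0, 2, 4, 11) | 4 | 3 | 2 | 0.38 |

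The two-knot fit equals the straight line. A natural-spline routine given only the two knots 2 and 4 returned 3 df, because it adds boundary knots itself. The same sentence can therefore produce the first or the last row, depending on the software.

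**Step 3: ties.** An index of 11 components probably takes few distinct values. Under assumed Poisson shapes with means 1, 2, 3 and 4, the tertiles fall at (0, 1), (1, 2), (2, 4) and (3, 5). With mean 1 the lower tertile is the minimum, so it coincides with a lower boundary knot. Three distinct knots remain, and the spline has 2 df instead of 3.

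**Step 4: the arm effect.** Write A for arm (0 or 1) and M for MSK-FI. The model as listed is

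logit(p) = strata + β·A + f(M).

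The log odds ratio between arms at any M is [β + f(M)] − f(M) = β. It is constant whatever the knots. With interaction terms g(M)·A it becomes β + g(M), which can vary.

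**Step 5: cost in df.** Three knots use 2 df for f and 2 for g, so 2 + 2 = 4 for MSK-FI, against 1 on the literal reading. Four knots would use 3 + 3 = 6.

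**The case against.** The strongest defence is that the plan never says the tertiles are the only knots. Treating named knots as interior and adding boundary knots at the data extremes is a common convention, and the sentence's own purpose favours that reading. This stands. A reader might infer that the planned model must be a straight line and cannot show non-linearity. The documents do not support that: it holds only if the two tertiles are the full knot set. The defence does not supply what is missing, though, because nothing in the plan says which reading applies.

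A second defence is that plotted risks curve even when the predictor is linear, and that the gap between the two risk curves varies with baseline risk even under a constant odds ratio. Both are true, but that shape is imposed by the logit link and not learned from the data.

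A third is that the knots matter less than the interaction. A linear MSK-FI term with an arm interaction could show a small difference at average risk and a larger one at high risk, whereas extra knots without an interaction leave the odds ratio constant. This is correct, and it is why both parts need attention. It could also be said that the stated aim and the two-arm plot imply an interaction. They may, but the listed model terms do not include one.

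A reader might also take the index to run from 0 to 11. The only such range in the documents (section 3.1) belongs to the Modified Frailty Index, a different instrument.

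**Conclusion.** The concern holds in a limited form. The spline is under-specified: it is a 1-df line on the log-odds scale if the tertiles are the complete knot set, and a 3-df curve with 2 non-linear terms if boundary knots are added at distinct values. The first contradicts the stated purpose; the second is not stated. Separately, the listed model has no arm-by-MSK-FI term, so the arm odds ratio is constant and the model cannot show whether relative value depends on risk, under either knot reading.

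The two-knot result and the constant odds ratio are exact and need no assumption about the index. The residual sums of squares and the tie examples rest on an assumed range and assumed distributions and are illustrative. How much the fitted curves would differ in this trial cannot be computed, because the documents give neither the MSK-FI distribution nor the expected event rate.

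The consequence is confined to an exploratory analysis. Section 4.2 describes the secondary aims as gathering preliminary data, and section 3.1 calls the study a pilot. No decision rule rests on these curves, and the feasibility rule and sample size are unaffected.

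**What to change.** Amend the baseline-risk paragraph in section 11.0 as follows:

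- State the total number of knots, at least three, and their positions, saying whether boundary knots are included. Three knots at the 10th, 50th and 90th percentiles of MSK-FI would be one choice; named index values would be another.
- State the MSK-FI score range, and give a rule for knots that coincide with each other or with the minimum. Settle the final positions from the pooled baseline distribution, without reference to arm or outcome.
- Include arm-by-MSK-FI spline terms, so that the arm effect can vary with baseline risk and the two curves can differ in shape.
- Apply the same specification to patient-reported and clinician-assessed recovery.

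The change is to wording only; no new data are needed. The statistical cost is that, with three knots and the interaction, MSK-FI uses 4 df instead of the 1 df of the literal reading, three more in all. The confidence bands will be wider, particularly at the extremes of the index where patients are likely to be few, and the curves should be presented as exploratory.

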The eRFA contains 28 questions about functional status, cognition, social support, social activity interference, emotional status, nutrition, vision, hearing and polypharmacy. On average, it takes between 10 to 20 minutes to complete. The eRFA is accessible using computers, tablets, and smartphones. It is partially integrated with the electronic medical record (EMR), with patients' names and medical record numbers pulled from the EMR as patient-specific questionnaires are generated.

The components of the eRFA, the 12 major instruments utilized, and the cutoff for significantly abnormal values are shown in figure 2.

Figure 2. Twelve major instruments of Electronic Rapid Fitness Assessment (the eRFA)

Domain	Instrument	Completed by	Description	Score range	Frail values
Functional Domain	Activities of Daily Living (ADL) [20]	Patient	Basic Activities of Daily Living (bADL or ADL) assesses patients' level of independence in 7 activities: bathing, dressing, grooming, feeding, bladder and bowel control, and walking inside and outside of the house. Answer choices to each are: limited a lot (0), limited a little (1), not limited (2).	0-14	≤13
	Instrumental Activities of Daily Living (iADL) [21]	Patient	Instrumental Activities of Daily Living (iADL) assesses patients' level of independence in 8 activities: telephone use, doing laundry, shopping, preparing meals, doing housework, handling own medications, handling money and finances, and transportation. Answer choices to each are: unable to do (0), able with some help (1), able without help (2).	0-16	≤15
	Karnofsky Performance Status (KPS) [22]	Patient	Karnofsky Performance Status rates patient's functional independence in performing ordinary tasks. The score ranges from 100 (Normal with no symptoms) to 0 (Dead) in increments of 10.	30-100	≤80

The patient-rated KPS is answered in 8 levels:

			100- Normal, no symptoms 90- Able to carry on normal activity, minor symptoms 80- Normal activity, with effort, some symptoms of disease 70- Can care for self, but unable to do normal activity or work 60- Require occasional assistance, but able to care for most needs 50- Require considerable assistance 40- Disabled, require special care and assistance 30- Severely disabled, require continuous nursing care		
	Fall in the past year	Patient	The number of falls in the past year	None, One time, More than one time	≥ 1 time

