To compare, by intervention arm, postoperative functional recovery. We will consider postoperative functional recovery as reported by the patient, as well as assessed by the study team during the 2nd study visit. Patient-reported recovery will be measured by three domains reported on both pre and post-operatively: Karnofsky Performance Status, basic activities of daily living, and instrumental activities of daily living.

Clinician-evaluated functional recovery will be assessed through the Timed Up and Go

test and the 4MWT. This analysis will only be done for patients who have completed the assessment during in-person visit with the surgery team. Recovery of Karnofsky Performance status, defined as the same or better Karnofsky Performance status during the 2nd study visit compared to baseline, will be compared between groups using a logistic regression with randomization strata as covariates. Basic activities of daily living, instrumental activities of daily living, Timed up and Go test and 4MWT will be compared between groups by ANCOVA, with baseline score and randomization strata as a covariate.

In the case that patient's surgery occurs after two months of completing the eRFA, either the patient has to complete another eRFA within two months of surgery, which then will be the patient's new preoperative baseline eRFA, or in case of not completing the eRFA, the patient will be excluded from the study.

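### Karnofsky status is the only functional scale compared solely as yes/no recovery, which discards the size of the change and can cost power

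*Combined protocol and SAP*

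**What the plan says.** Section 11.0 (Secondary Aims, functional recovery) names five scales: KPS, basic and instrumental activities of daily living (bADL, iADL), Timed Up and Go (TUG) and the 4-meter walk test (4MWT). For KPS the endpoint is "Recovery of Karnofsky Performance status, defined as the same or better Karnofsky Performance status during the 2nd study visit compared to baseline", and it "will be compared between groups using a logistic regression with randomization strata as covariates". The next sentence says that the other four scales "will be compared between groups by ANCOVA, with baseline score and randomization strata as a covariate".

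The same section then builds three-category outcomes (complete, partial, no recovery). One uses KPS, bADL and iADL; the other uses TUG and 4MWT. On these it says: "We will test the association between intervention arm and degree of recovery by using ordinal regression with randomization strata as covariates". For the other four scales this comes on top of the ANCOVA. KPS has no score-based comparison anywhere.

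Section 3.1, Figure 2, describes the scale: "The patient-rated KPS is answered in 8 levels", from 30 to 100 in steps of 10. The Sample size part of Section 11.0 gives a power table for the continuous secondary endpoints under ANCOVA: "Assuming a correlation of 0.5 between baseline and follow-up, and a standard deviation of 1.8", the latter "as seen in our preliminary dataset for the basic activities of daily living, the score of which ranges from 0 to 14". It gives no power, standard deviation, correlation or recovery rate for KPS.

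**The concern.** The cut treats a 10-point fall and a 50-point fall as the same failure, and a gain the same as no change. It also ties the outcome to the starting level: a patient who starts at 100 can only hold or fall, while a patient who starts at 60 has room to rise. Baseline KPS enters only through the definition of recovery, not as a covariate. The number-of-impairments stratum (Section 12.3) carries part of that information, since a low KPS counts as one impairment.

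Functional recovery is Aim 3, and KPS is one of its three patient-reported domains. A real difference in KPS could be missed although the trial already holds the data to look for it more efficiently. The KPS estimate would also be an odds ratio that cannot be set beside the score differences reported for the other scales.

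**Working it through.** **Inputs from the documents.** About 95 patients per arm, baseline to follow-up correlation r = 0.5 and SD 1.8 (a bADL figure), all from Section 11.0, Sample size. KPS has eight levels (Section 3.1, Figure 2). Alpha is not stated for the power table; two-sided 5% is used because it reproduces the table.

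**Assumed.** KPS means, SDs, correlation, recovery rates and effect pattern. None is in the documents.

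**1. The plan's own table.** The ANCOVA residual SD is 1.8 × √(1 − 0.5²) = 1.559. The standard error is 1.559 × √(2/95) = 0.226. Power is Φ(difference/0.226 − 1.96).

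| Difference | Stated | Recomputed |
|---|---|---|
| 0.5 | 60% | 59.9% |
| 0.67 | 84% | 84.2% |
| 0.8 | 94% | 94.3% |

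The table reproduces. One-sided 5% would give 71%, 91% and 97%, which does not fit.

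**2. The cut on a continuous score.** With r = 0.5 the change score has SD 1.8 × √(2 × (1 − 0.5)) = 1.8. If the control arm recovers with probability p, the other arm recovers with probability Φ(Φ⁻¹(p) + difference/1.8). At p = 50% this gives 61%, 65% and 67%. A two-proportion test with 95 per arm then has power of 32.8%, 52.5% and 67.3%, or 27, 32 and 27 points below ANCOVA. Over control recovery rates of 20% to 80% the loss is 26 to 46 points. This is only a rough guide, because KPS is coarse and capped and ties count as recovery.

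**3. An eight-level, capped KPS.** Simulation with latent normal scores rounded to tens and capped at 100, 95 per arm, 1,500 runs per setting (Monte Carlo standard error at most √(0.25/1500) = 1.3 points). The arm effect is a uniform shift of the same standardised size as the plan's table rows: at SD 15, 15 × 0.5/1.8 = 4.2 points, and likewise 5.6 and 6.7. The rows below assume baseline mean 90, SD 15 and a mean fall of 10.

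| r | Shift | Recovery, two arms | ANCOVA | Yes/no | Yes/no + baseline | Loss, yes/no vs ANCOVA |
|---|---|---|---|---|---|---|
| 0.5 | 5.6 | 42% / 57% | 78.4% | 57.5% | 60.8% | 21 |
| 0.5 | 6.7 | 42% / 60% | 90.1% | 72.2% | 75.8% | 18 |
| 0.7 | 4.2 | 40% / 54% | 66.4% | 48.7% | 50.7% | 18 |
| 0.7 | 5.6 | 40% / 59% | 89.1% | 74.8% | 75.1% | 14 |
| 0.7 | 6.7 | 40% / 63% | 96.9% | 87.9% | 89.0% | 9 |

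Over all settings tried (mean 80 or 90, SD 10 or 15, mean fall 0 to 10) the loss was 16 to 33 points at r = 0.5 and 9 to 29 at r = 0.7. Separate simulations with other assumed means and SDs and shifts of 5 to 6 points gave 56–60% against 73–79%, 58–74% against 81–89%, and 57–78% against 75–92% at r = 0.5. At r = 0.7 they gave losses of 9 to 18 points. Type I error was about 5% for every method.

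**4. Where the loss comes from.** In the table above, adding baseline KPS to the logistic model gains 0.3 to 3.6 points. Elsewhere the change was about −1 to +5 points. The covariate matters for a score: on the continuous scale, a change-score comparison without it has 48.2% power at a difference of 0.5, against 59.9% for ANCOVA. It does little once the outcome has been cut.

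**5. A different effect pattern.** Suppose full return to baseline rises from 45% to 65%, and falls among the remaining patients keep the same distribution (10, 20 or 30 points). The pooled proportion is 0.55, with null standard error √(2 × 0.55 × 0.45/95) = 0.0722. The standard error under the alternative is √((0.45 × 0.55 + 0.65 × 0.35)/95) = 0.0707. Power of the yes/no test is Φ((0.20 − 1.96 × 0.0722)/0.0707), about 80%. ANCOVA reached 66–67% in simulation. If the benefit only prevents 10-point falls, simulation gave 80% for yes/no and 17% for ANCOVA.

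**The case against.** The aim is functional recovery, and return to baseline is a legitimate estimand with its own meaning; it also matches the three-category outcomes. A power comparison under a uniform shift favours ANCOVA by construction, and step 5 shows the ranking can reverse. KPS is a single ordered item, so declining to treat it as continuous is defensible. The plan makes no power claim for KPS, ties no decision to it, and describes the secondary aims as preliminary data in a pilot.

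Much of this stands. The loss is conditional on the effect pattern, and the stakes are modest. Two parts do not. Coarseness cannot be the plan's reason: Figure 2 gives the TUG score range as three bands (although it also says the time is recorded), and TUG still gets ANCOVA. A proportional-odds model would also respect the ordering without cutting to two levels. Nor does the plan say that it expects an effect on full return only.

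A reader might infer more than the documents support:

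- **A fixed loss, such as 15 to 20 points.** No KPS input is given, and r = 0.5 is stated for the continuous endpoints beside a bADL SD.
- **That the missing covariate is the cause.** Step 4 shows otherwise, and baseline KPS does define the outcome.
- **Bias.** Ceiling effects and regression to the mean act on both randomized arms alike.
- **That KPS is the only scale ever categorised, or that the three-category regressions need baseline scores added.** The other scales are categorised too, in addition to their ANCOVA. No calculation supports changing those regressions, and the nearest evidence, from the logistic model, shows little gain.

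**Conclusion.** The point holds as a conditional loss of efficiency in one secondary endpoint. Among the scale-by-scale comparisons, KPS alone is analysed only as yes/no and alone lacks its baseline score as a covariate, without a stated reason. If the arms differ by a general shift in KPS, the planned test gives up roughly 10 to 30 points of power against ANCOVA with baseline. That range rests on 95 per arm, r of 0.5 to 0.7, and assumed KPS means, SDs and effects. If the arms differ mainly in full return to baseline, the yes/no test can be the stronger one. The planned test is valid, and the primary feasibility conclusion does not depend on it.

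**What to change.** In Section 11.0, make the main KPS comparison one of second-visit KPS between arms, with baseline KPS and randomization strata as covariates. Use either the same ANCOVA as the other scales or a proportional-odds model on the eight levels, and name which one in advance. Keep the same-or-better proportion by arm as a supportive summary, with baseline KPS added to its logistic model. Leave the three-category regressions as they are. If the investigators expect the effect to fall mainly on full return to baseline and prefer yes/no as the main analysis for that reason, the plan should say so.

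The cost is one or two sentences and no new data, since the eRFA, which includes KPS, is already scheduled before surgery and at the second visit (Section 9.0). The downside is one more analysis of a secondary endpoint, and a main KPS estimate that becomes a score difference or common odds ratio instead of a recovery proportion.
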